4.9.2. Handling of Concomitant Therapies/Medications with Missing/Partial Dates

Concomitant medications are defined in Section 5.6.8. Concomitant therapies/medications with start dates that are completely or partially missing will be handled as follows for the propose of determining concomitance.

1. If the start date has the month and year but the day is missing, the therapy will be considered concomitant if the month and year are:
 - a. On or after the month and year of the date of the first dose of study treatment
 - b. On or before the month and year of the date of the last dose of study treatment plus 30 days
2. If the start date has the year, but the day and month are missing, the therapy will be considered concomitant if the year is:
 - a. On or after the year of the date of the first dose of study treatment
 - b. On or before the year of the date of the last dose of study treatment plus 30 days.
3. If the start date of concomitant therapies is completely missing and the stop date of concomitant therapies is prior to the date of informed consent, then this therapy will not be considered concomitant.
4. If the start date of concomitant therapies is completely or partially missing and the stop date of concomitant therapies is on or after the date of the first dose of study treatment, then the therapy will be considered concomitant.
5. If the start date and stop date of concomitant therapies are completely missing, then the therapy will be considered concomitant if the therapy was reported as a concomitant therapy.

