### **11.2.8. 2-Year Survival Check-In**

Sites will document participant's survival status approximately 2 years after the participant's first dose of study treatment. If the participant discontinues from study treatment prior to the 2-year check-in, quarterly telephone or email contact following EOT is required until the 2-year survival data point has been collected. Additionally, collection of subsequent anticancer therapy after nirogacestat and overall response to this therapy will be recorded. Only information about the subsequent therapy used directly after nirogacestat is required along with the final survival outcome at the 2-year check point.

A copy of the telephone report or email must be documented in the source documentation and the survival data point will be captured in the eCRF.

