5.6.8. Concomitant Medications

Any medication or vaccine (including over-the-counter or prescription medicines, vitamins, and/or herbal supplements) that the participant is receiving at the time of informed consent and/or receives during the study through 30 days after the last dose of study treatment will be recorded along with:

- Reason for use;
- Dates of administration including start and end dates; and
- Dosage information including dose and frequency.

Concomitant medications will be coded using the WHO Drug Dictionary March 2022 version or higher. Medications or vaccines that ended before receiving the first study treatment will be considered as the prior medication. Medications or vaccines that continued or started on or after receiving the first dose through 30 days after the last dose of study treatment will be summarized as the concomitant medication. Medication, vaccine or procedure started more than 30 days after the last dose will be considered as subsequent.

The handling of partial/missing start dates for concomitant therapies/medications are described in Section 4.9.2. Concomitant medications will be tabulated by anatomic therapeutic class (ATC) and PT. In these tabulations, each participant will contribute only once to each ATC and PT regardless of number of uses.

The concomitant procedures will be coded using the MedDRA coding dictionary version 27.0 and displayed in tables and data listings using system organ class (SOC) and preferred term (PT).

All medications, vaccines and procedures will be included in data listings. An identifier will be used to show whether a medication, vaccine or procedure was prior, concomitant or subsequent.

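### SAP 4.9.2 rules 1 and 2 can class a drug stopped before first dose as concomitant, against the definition in SAP 5.6.8, and rule 4 omits ongoing drugs

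*SAP*

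**What the plan says.** SAP 4.9.2 sets rules for medications with missing or partial start dates and refers to SAP 5.6.8 for the meaning of concomitant. Section 5.6.8 gives three classes:

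- Prior: "Medications or vaccines that ended before receiving the first study treatment will be considered as the prior medication".
- Concomitant: "Medications or vaccines that continued or started on or after receiving the first dose through 30 days after the last dose of study treatment".
- Subsequent: started more than 30 days after the last dose.

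The rules in 4.9.2 are these:

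- Rule 1 (day missing): concomitant if the start month and year are (a) "On or after the month and year of the date of the first dose of study treatment" and (b) "On or before the month and year of the date of the last dose of study treatment plus 30 days". The two items are listed with no joining word.
- Rule 2 (day and month missing): the same test by year, with item (a) reading "On or after the year of the date of the first dose of study treatment".
- Rule 3: not concomitant if the start date is "completely missing and the stop date of concomitant therapies is prior to the date of informed consent".
- Rule 4: concomitant if the start date is partly or completely missing and there is a stop date on or after first dose.
- Rule 5: if both dates are completely missing, concomitant if it was reported as such.

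No rule in 4.9.2 mentions a medication that is ongoing.

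**The concern.** Section 4.9.2 should apply the 5.6.8 definition to incomplete dates, not change it. Under 5.6.8 the stop date separates prior from concomitant. Rules 1 and 2 never consult the stop date, even when it is fully known, so a definite fact about the record is overridden by an inference from an incomplete start date.

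Rule 4 has the opposite weakness. It recognises continued use only through a recorded stop date, so the same long-standing drug is covered if it was stopped during the trial and not covered if it was never stopped.

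At stake is the accuracy of the concomitant-medication tables by ATC class and preferred term, and of the identifier in the listings. These describe background treatment in a trial whose protocol restricts or cautions about acid-reducing agents and drugs acting on CYP3A4 or P-gp.

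**Working it through.** The plan states no figure on this point, so the check applies both sections to test records. The dates are assumptions: consent 20 February 2023, first dose 15 March 2023, last dose 10 January 2024. The concomitant window then ends at 10 January + 30 days = 9 February 2024. Items (a) and (b) are both required, and an ongoing drug has no stop date.

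| Record | SAP 5.6.8 | SAP 4.9.2 |
|---|---|---|
| A. Start March 2023 (day missing), stop 10 March 2023 | Prior (10 March is before 15 March) | Concomitant, rule 1 |
| B. Start 2023 (day and month missing), stop 10 March 2023 | Prior | Concomitant, rule 2 |
| C. Start June 2019 (day missing), ongoing | Concomitant (continued) | No rule reaches it |
| D. Start 2019 (day and month missing), ongoing | Concomitant (continued) | No rule reaches it |
| E. Start June 2019 (day missing), stop 1 August 2023 | Concomitant | Concomitant, rule 4 |
| F. Start completely missing, stop 1 March 2023 | Prior | No rule reaches it |

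**A and B.** For A, March 2023 is not before March 2023 (item a) and not after February 2024 (item b), so rule 1 fires. For B, 2023 is not before 2023 and not after 2024, so rule 2 fires. Rule 3 does not apply, because part of the start date is known. Rule 4 does not apply, because the stop is before first dose.

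**C and D.** Item (a) fails, rule 4 finds no stop date, and rule 5 needs both dates completely missing.

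**F.** Rule 3 looks for a stop before consent, and 1 March is after 20 February. Rule 4 looks for a stop on or after first dose, and 1 March is before 15 March. The interval between consent and first dose is uncovered.

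**Other readings.** If (a) and (b) are alternatives, every start date meets at least one of them, so C and D are counted only because the test has become empty. If ongoing is read as a stop date after first dose, rule 4 catches C and D. Neither reading changes A or B.

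**Size.** Protocol 8.3 and SAP 5.6.8 record medications in use at consent or later, and screening lasts up to 28 days unless extended. The A/B error therefore needs a partial start date in the month or year of first dose and a stop between consent and first dose. With the 53 enrolled participants in SAP 5.8 as denominator, each one misplaced shifts a row by 1/53 = 1.9 percentage points.

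**The case against.** The strongest reply concerns ongoing drugs. Rules 1, 2, 4 and 5 say when a therapy is concomitant, not that it is concomitant only then. Rule 3 alone excludes anything. Section 4.9.2 defers to 5.6.8, which includes medications that continued. A June 2019 start precedes first dose whatever the missing day, so no imputation is needed. SAP 5.6.3 also gives ongoing medications a later end date when duration of use is calculated. Most of this stands: a programmer following the definition would keep records C and D. What remains is a drafting gap. The 5.6.3 convention is not carried into 4.9.2. By contrast, the adverse-event rule in SAP 4.9.1 asks only that the end date not precede first dose, which an ongoing event satisfies.

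The reply does not help with A and B. There rules 1 and 2 do fire, and they give an answer that 5.6.8 contradicts. That few records are affected is a fair point about size, not about correctness.

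A reader might also infer a contradiction over next-line cancer therapy begun within 30 days of the last dose, because the protocol's 2-year check-in provides that "collection of subsequent anticancer therapy after nirogacestat and overall response to this therapy will be recorded", with no 30-day limit. The documents do not support that. SAP 5.6.8 says "Medication, vaccine or procedure started more than 30 days after the last dose will be considered as subsequent", so therapy started on 30 January 2024 (day 20 after last dose) is concomitant under 5.6.8 and under 4.9.2 alike. The restriction in Protocol 8.3.2 and Table 6 runs until study treatment ends, so this label does not imply a breach of it. PFS2 and the Table 3 censoring rule depend on the therapy itself, not on this label.

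**Conclusion.** The point holds as a minor inconsistency. Rules 1 and 2 misclassify drugs with a known stop before first dose under every reading tested, and rule 3 cannot repair it because of its start-date condition and its link to consent. The lack of cover for ongoing drugs in rule 4 is a gap in wording that the governing definition can fill.

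A reader might infer that every long-standing ongoing drug is lost, or that table rows are undercounted by some definite share. The first goes too far for the reason given above. For the second, the documents do not say how often start dates are partial, so no share can be given. Nor is this the only summary of such treatment: SAP 5.6.3 plans separate concomitant-medication summaries for five safety topics, and all medications are listed.

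The consequence is limited to the descriptive tables and the listing identifier. ORR, PFS-6, DoR, OS and PFS2 do not use the classification. The 1.9-point figure assumes that all 53 enrolled participants form the table denominator. The test dates are illustrative.

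**What to change.** In SAP 4.9.2, add a step before rules 1 and 2 that compares stop date or ongoing status with first dose:

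- A known stop before first dose makes the therapy prior.
- A therapy started before first dose and marked ongoing, or with a stop on or after first dose, is concomitant.
- Only records not settled by that step go on to rules 1 and 2.

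State that items (a) and (b) are both required. Change the reference date in rule 3 from informed consent to first dose, which also closes the gap shown by record F.

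A record with a partial start date, no stop date and no ongoing mark should be queried rather than counted automatically, so that the change does not replace an undercount with an overcount.

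The cost is a few sentences of SAP text and a small program change. No new data item is needed, and no efficacy output changes.

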4.9.3. Handling of Missing Dates for Disease History and Prior Therapies

To calculate time from diagnosis or most recent prior therapy to informed consent, partial/missing dates for diagnosis and last prior therapy completion will be imputed as follows:

- If both day and month are missing and the year is prior to the year of screening, the imputed day and month will be July 1.

- If both day and month are missing and the year is the same as the year of screening, the imputed date will be the middle point between January 1 of the year and the screening date. If the middle point falls between two dates, the first of the two dates will be used.
- If day is missing and the month and year are prior to the month and year of screening, the imputed date will be 15th day of the month.
- If day is missing and the month and year are the same as the month and year of screening, the imputed date will be the middle point between the first date of the month and the screening date. If the middle point falls between two dates, the first of the two dates will be used.
- No imputation will be performed if the year is missing.

4.10. Visit Windows

No visit windowing was performed. All visits will be tabulated per the evaluation visit as recorded on the eCRF. Repeat, retest, and unscheduled assessments will not be considered for the calculation of summary statistics and figures, unless assessment qualifies as baseline, or otherwise indicated. These types of assessments will be included in the listings.

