### 12.3.2. Safety Analyses

All safety analyses will be performed on participants who received at least one dose of nirogacestat.

The safety and tolerability of nirogacestat will be evaluated by means of treatment-emergent AEs, physical examinations, and laboratory safety evaluations. Adverse Events will be graded by the Investigator according to the CTCAE v5.0 and coded using the Medical Dictionary for Regulatory Activities.

The focus on AE summaries will be on Treatment-Emergent AEs, those with initial onset or increasing in severity after the first dose of study treatment through 30 days after the last dose of study treatment. The number and percentage of participants who experienced an AE, SAE,

treatment related AE, and treatment related SAE will be summarized according to worst toxicity grades.

Summaries of clinical laboratory parameters will be summarized by study visit and overall, including absolute results and changes from baseline. Tables for the shift in CTCAE severity grade of laboratory data from baseline to the worst post-baseline value and from baseline to each visit will be presented.

Vital signs data will be summarized by study visit and overall using descriptive statistics. Summaries will be presented for the observed value, the change from baseline value, and the change from baseline to the worst post-baseline value during the treatment period.

The observed ECG values and change from baseline values, and the change from baseline to the worst post-baseline value during the treatment period will be summarized descriptively. The overall ECG assessments will be summarized categorically (normal, abnormal without clinical significance, and abnormal with clinical significance) as a shift table by study visit.

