5.6.4. Protocol-Required Laboratory Assessments

Protocol-required laboratory parameters are listed in Table 13-1 in the protocol. The tests in this table will be performed by the local laboratory except for follicle-stimulating hormone (FSH), luteinizing hormone (LH), estradiol, progesterone, Inhibin A, Inhibin B, Anti-Mullerian hormone/Mullerian inhibiting substance (AMH/MIS), and CA-125, which will be sent to a central laboratory.

Clinical laboratory values will be expressed in international system of units (SI) units. Summaries of clinical laboratory parameters will be summarized by study visit and overall. Tables for the shift of laboratory data from baseline to the worst post-baseline value will be presented for each lab parameter. The shift from baseline to each visit will also be presented for hematology and chemistry parameters.

The actual value and change from baseline will be summarized for each visit for clinical hematology and chemistry. For analysis of tumor markers and hormones, see Section 5.5.3.

Laboratory results will also be summarized by maximum CTCAE grade as available. For lab tests with NCI – CTCAE classification, the shift from baseline to each post baseline visit and the maximum (worst) post baseline grade will be tabulated. Shift tables will summarize the count and frequency of each baseline CTCAE grade to the highest CTCAE grade on study. Laboratory tests with bi-directional grades will be presented separately for each direction (e.g., hyperglycemia and hypoglycemia). For lab tests without NCI – CTCAE classifications, the shift from baseline to each post baseline visit and the worst post-baseline value (high or low) will be summarized using the lab range indicators (normal, high, or low).

Additional shift tables will be produced for ALT, AST, alkaline phosphatase, bilirubin, phosphorus, and creatine showing shifts of below normal range, within normal range, >1 to $2 \times$ upper limit of normal range, >2 to $3 \times$ upper limit of normal range, >3 to $5 \times$ upper limit of normal range, to $> 5 \times$ upper limit of normal range from baseline to the worst (highest) post baseline value.

Box and whisker plots displaying the values over time by nominal visit will be produced for the hematology and clinical chemistry lab tests.

All laboratory results will be listed and laboratory tests with an abnormal result will be flagged. A subset listing will be presented for all grade 3 or higher laboratory values.

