5.6.6. Electrocardiogram

The actual value and change from baseline at each time point will be summarized for 12-lead ECG parameters. The 12-Lead ECG parameters include heart rate, PR, RR, QRS, QT and QTcF intervals.

Categorical groups of QTcF will be summarized as follows:

- Maximum post-baseline QTcF
 - ≤ 450 msec
 - > 450 and ≤ 480 msec
 - > 480 and ≤ 500 msec
 - > 500 msec

- Maximum change from baseline for QTcF
 - ≤ 30 msec
 - > 30 and ≤ 60 msec
 - > 60 msec
- Baseline QTcF < 450 msec and post-baseline QTcF > 500 msec
- Baseline QTcF between 450 and 480 msec and post-baseline QTcF ≥ 530 msec

ECG parameters will be summarized by visit and the worst post-baseline change from baseline. All ECG data will be included in a by-participant data listing. Listings will be provided for participants with abnormal or outlying values for QTcF and changes in QTcF.

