5.6.7. Vital Signs

The actual value and change from baseline for all parameters (blood pressure, respiratory rate, heart rate, and body temperature) will be summarized at each scheduled visit.

Potentially clinically significant post-baseline vital signs will also be summarized following the criteria as below:

- Systolic Blood Pressure (mmHg)
 - Value ≥ 150
 - Increase of 20 from baseline
 - Value ≥ 150 and increase of 20 from baseline
 - Value < 90
 - Decrease of 20 from baseline
 - Value < 90 and decrease of 20 from baseline
- Diastolic Blood Pressure (mmHg)
 - Value ≥ 95
 - Increase of 10 from baseline
 - Value ≥ 95 and increase of 10 from baseline
 - Value < 60
 - Decrease of 10 from baseline
 - Value < 60 and decrease of 10 from baseline

- Heart Rate (beats/min)
 - Value ≥ 110
 - Increase of 20 from baseline
 - Value ≥ 110 and increase of 20 from baseline
 - Value ≤ 50
 - Decrease of 20 from baseline
 - Value ≤ 50 and decrease of 20 from baseline
- Temperature (°C)
 - Value ≥ 38
 - Value < 35

Vital sign measurements will be summarized by visit and the worst post-baseline change from baseline. The data listing will be presented for each participant. A summary table and listing will also be provided for participants with potentially clinically significant vital signs.

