8.4.2.10. Diarrhea

The Diarrhea search definition is based on the MedDRA version 27.0 PT of Diarrhoea.

Plan Version History

Version	Effective Date	Changes	Author / Modified by
1.0	17-Feb-2023	NA	[name]
2.0	03-Jun-2024	See summary below	[name]
3.0	28-Oct-2024	See summary below	[name]

Change History Summary

Version	Modifications
1.0	Initial Version
2.0	PFS-6 was redefined as a survival probability for consistency with the Kaplan-Meier methodology which was intended to be used to estimate this endpoint.
2.0	Definitions and analysis methods were added for PFS and OS.
2.0	Progression-free survival on continued nirogacestat treatment and PFS2 were added due to protocol amendment.
2.0	Miscellaneous formatting and typographical changes.
2.0	Statement was added for why the planned interim assessment using Bayesian approach as mentioned in the protocol was not performed.
2.0	Analysis of safety topics of special interest identified using standardized MedDRA queries (SMQ) or customized MedDRA queries was added.
3.0	Section 5.6.2 - Added a summary table for serious TEAEs by maximum severity (Grade)
3.0	Section 5.6.6 - Rows for the worst post-baseline change from baseline added to the ECG summary table.
3.0	Section 5.6.7 - Rows for the worst post-baseline change from baseline added to the vital signs summary table.
3.0	Section 8.4.1.4 Electrolyte disorder PTs were revised. Added new electrolyte disorder analyses (summary table and shift table).

Certificate Of Completion

Envelope Id: 40641299A5654F08AF98E3810FA56FF4

Status: Completed

Subject: Complete with DocuSign: NIR-OGT-201 SAP V3.0 28Oct2024.pdf

Source Envelope:

Document Pages: 100

Signatures: 4

Envelope Originator:

Certificate Pages: 5

Initials: 0

[name]

AutoNav: Enabled

[name]

Enveloped Stamping: Disabled

5th Floor

Time Zone: (UTC-05:00) Eastern Time (US & Canada)

[name]

[contact]

IP Address: [name]

Record Tracking

Status: Original

Holder: [name]

Location: DocuSign

29-Oct-2024 | 10:33

[contact]

Signer Events**Signature****Timestamp**

[name]

[name]

Sent: 29-Oct-2024 | 10:37

[contact]

Viewed: 29-Oct-2024 | 10:37

Security Level: Email, Account Authentication
(Required)

Signed: 29-Oct-2024 | 10:38

Signature Adoption: Pre-selected Style

Signature ID:

FC9A7027-5907-4B62-B0EB-8FAC79DE2641

Using IP Address: [name]

With Signing Authentication via DocuSign password

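### SAP 4.10 keeps off-schedule results out of summary statistics and no section expressly exempts the worst-value safety tables; read literally, off-schedule extremes drop out

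*SAP*

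**What the plan says.** SAP 4.10 (Visit Windows) tabulates visits as recorded on the eCRF and then states: "Repeat, retest, and unscheduled assessments will not be considered for the calculation of summary statistics and figures, unless assessment qualifies as baseline, or otherwise indicated". The excluded results go to the listings.

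The SAP sections that rely on extremes say:

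- **ECG (5.6.6):** "ECG parameters will be summarized by visit and the worst post-baseline change from baseline". The section also tabulates categories of maximum post-baseline QTcF and of maximum QTcF change.
- **Vital signs (5.6.7):** "Vital sign measurements will be summarized by visit and the worst post-baseline change from baseline". It also counts potentially clinically significant values. The plain by-visit summary is worded separately: values "will be summarized at each scheduled visit".
- **Laboratory (5.6.4):** worst-value shifts for each parameter, and "Shift tables will summarize the count and frequency of each baseline CTCAE grade to the highest CTCAE grade on study". A further table counts participants who meet the liver chemistry stopping criteria.

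The Change History Summary records the ECG and vital-sign items as version 3.0 additions: "Rows for the worst post-baseline change from baseline added to the ECG summary table" and "Rows for the worst post-baseline change from baseline added to the vital signs summary table".

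Protocol 12.3.2 promises, for vital signs and for ECG, "the change from baseline to the worst post-baseline value during the treatment period".

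**The concern.** The rule in 4.10 covers summary statistics in general and is not limited in words to by-visit tables. A worst-value table exists to show the most extreme result a participant had. Extremes are often found, or checked, off schedule. Protocol 8.4 allows unscheduled visits at any time, 11.2.3 allows vital signs to be repeated, 11.2.5 has clinically significant abnormal laboratory results repeated, and 9.1.2 calls for triplicate ECGs when a QTcF criterion is met.

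If a programmer applies 4.10 as written, those results do not reach the worst-value tables. If another programmer takes the word *worst* as its own exemption, they do. Both could claim to follow the SAP, and the first would report a milder safety profile from the same data.

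**Working it through.** There is no plan figure to reproduce. The check compares the passages and counts scheduled readings.

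**1. Is there an express exemption?** 4.10 has two exceptions: the assessment qualifies as baseline, or something else is indicated. Sections 5.6.4, 5.6.6 and 5.6.7 nowhere say that repeat or unscheduled results count toward a worst, maximum, highest-grade or outlier analysis. 4.10 is the only SAP text found that says how unscheduled results are treated in summaries.

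**2. Direction of the effect.** Let S be a participant's scheduled post-baseline values and U the off-schedule ones.

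- High direction: max(S) ≤ max(S ∪ U).
- Low direction: min(S) ≥ min(S ∪ U).

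Baseline is the same either way, because 4.10 lets an off-schedule value serve as baseline. Dropping U therefore leaves the worst value unchanged or makes it less extreme, never more.

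**3. Exposure, from the protocol Schedule of Assessments (Table 2, footnotes 8a and 8b).**

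| | Scheduled after first dose, up to C13D1 (Day 337) | Later |
|---|---|---|
| Vital signs | C2D1 (1) + C3–C7 (5) + C8–C13 (6) = 12 visits | every 3 cycles, and EOT |
| ECG | C1D1 post-dose (1) + C2D1 pre- and post-dose (2) = 3 readings, all by Day 29 | EOT (1), safety FUP (1) |

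Scheduled ECG readings after first dose: 3 + 1 + 1 = 5, of which 4 fall no later than EOT. For a participant still on treatment at C13D1, the interval with no scheduled ECG is 337 − 29 = 308 days. Any ECG in that interval is off schedule, as are confirmatory triplicates. This assumes that assessments between planned visits are recorded as unscheduled or repeat. These are counts of readings, not of missed peaks.

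**4. Against the protocol.** Protocol 12.3.2 ties the worst ECG and vital-sign value to the treatment period and not to scheduled visits. It uses no such treatment-period wording for laboratory data and does not list the QTcF categories or vital-sign thresholds. The tension with the protocol is therefore confined to the worst-change analyses.

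**5. Against the SAP itself.** One item in the 5.6.4 liver-criteria table is ALT at or above 3 × ULN that cannot be monitored weekly for 4 weeks, with missing values treated as not monitored. Scheduled safety laboratory visits are 28 days apart up to C13D1 and 421 − 337 = 84 days apart from there to C16. Weekly results are necessarily off schedule. If 4.10 removed them, every participant with such an ALT value would appear unmonitored. That cannot be intended, so 4.10 cannot apply literally to every safety summary, yet the SAP leaves the reader to work this out.

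**The case against.** The best counter-argument is that 4.10 was never meant to reach these tables. It sits under Visit Windows, directly after a sentence on tabulating visits, so it can be read as governing nominal-visit statistics and plots only. Words such as *worst*, *maximum* and *on study* may themselves count as indicating otherwise, and 5.6.7 reserves scheduled-visit wording for its by-visit summary. The liver table supports this reading. The table shells are separate documents (SAP 8.3), were not available here, and may settle record selection. All of this stands as a possible reading; none of it is stated.

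A reader might go further and infer that the SAP plainly contradicts the protocol for the ECG and vital-sign worst-change rows, because the Change History Summary places them in the summary tables. The documents do not support that. The change history says where the rows sit, not which records feed them, and the rows use the same word *worst* as the laboratory shifts. Protocol 12.3.2 does not mention unscheduled results, and protocol 12.3 leaves data-handling procedures to the SAP. SAP Section 6 lists only notable changes, so its silence proves little.

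The effect is also limited. Off-schedule results remain in the listings. Dedicated listings are planned for outlying QTcF, for potentially clinically significant vital signs and for Grade 3 or higher laboratory values. New clinically relevant ECG findings are to be reported as adverse events (protocol 9.1.2), and liver-enzyme rises of Grade 2 or higher are AESIs (protocol Table 9). An abnormal value first found at a scheduled visit stays in the table in any case.

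**Conclusion.** The point holds as an ambiguity with a one-sided consequence. The stated default excludes off-schedule results from summary statistics, nothing expressly brings them back for the worst-value, maximum and outlier analyses, and literal application can only make those tables milder. It fits poorly with the plain meaning of protocol 12.3.2 for ECG and vital signs, and it cannot be squared with the liver-criteria table.

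Severity is minor and confidence is medium. The documents give no rate of off-schedule extremes, so the number of participants affected cannot be computed. A reader might infer from the 308-day ECG gap that peaks have been missed, or that the SAP created the gap. Neither follows: the gap comes from the protocol schedule, and 4.10 decides only whether an unscheduled ECG taken in it would count. The conclusion rests on the recording assumption above and on the shells not already resolving the matter.

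**What to change.** Amend SAP 4.10 along these lines:

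> Repeat, retest and unscheduled assessments are excluded from by-visit summaries and by-visit plots only, unless they qualify as baseline. Worst-value, maximum, highest-grade, outlier and liver-criteria analyses use all post-baseline results, scheduled or not (for ECG and vital signs, those within the treatment period of protocol 12.3.2).

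If a scheduled-only analysis is intended for ECG and vital signs, say so and list it in SAP Section 6.

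The cost is this short amendment and one record-selection flag in programming. No new data are needed, because 4.10 already sends these results to the listings. If the shells already use all records, the amendment only documents that.
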